## 5 Study Treatment

### 5.1 Treatment of lenvatinib

Lenvatinib will be given on a once a day daily basis in a 21-day cycle. Lenvatinib will be self-administered by patients orally once a day during the study period. Patients will self-administer lenvatinib at home, except on study visit days. On these visit days, patients should take lenvatinib after chemotherapy is administered. Patients will be instructed to take each dose orally once daily, with or without food, starting on day 1 of

cycle 1. The capsules should be swallowed whole without chewing, dissolving, or opening them. Patients should be instructed to take their dose of study drug at the same time each day. If the usual dosing time is missed, the patient should take the dose that day as soon as they remember as long as this is within 12 hours of the usual time the patient takes the dose. If it has been over 12 hours then this will be considered a missed dose. Patients should not make up missed or vomited doses; dosing should resume on the next calendar day unless otherwise instructed. Patients will be given a medication diary to record all doses taken, missed/skipped, or vomited. This diary will be reviewed with study personnel prior to dispensing medication for the next cycle.

## **5.2 Treatment eribulin**

Eribulin will be given as IV infusion or slowly infusion within 15 or 30 minutes in a 100 or 250ml of 0.9% NaCl solution. Eribulin will be given on days 1 and 8 of every 21-days cycle. Eribulin will be given prior to Lenvatinib administration on days 1 and 8. Each cycle will last 21 (+/- 3) days. Laboratory tests will be performed within 3 days prior to days 1 and 8 of all cycles to assess toxicity and confirm that it is safe to proceed with treatment (see Section 6.5) for a complete listing of assessments). The dose of eribulin will be calculated based on the BSA at study entry and should only be recalculated if there is >10% change in body weight from baseline. The actual body weight will be used for these calculations.

### **5.2.1 Ancillary and concomitant medications during eribulin treatment**

1. Intravenous antihistamine medication and/or steroids could be considered, but not necessary, before eribulin.
2. G-CSF could be administered subcutaneously or intravenously according to the Taiwan National Health Insurance Policy Guideline. The use of prophylactic G-CSF is at the investigator's discretion but would not be financially covered by the study.
3. Patients who are taking any herbal (alternative) medicines are NOT eligible for participation.
4. Patients who are undergoing concomitant radiotherapy or chemotherapy are NOT eligible for participation. Radiotherapy is not permitted during study
5. Bisphosphonate or other anti-resorptive agents are acceptable during the study treatment
6. Drug that would lead to QTc prolongation are prohibited during treatment (eg, arrhythmic drugs such as amiodarone, procainamide; antibiotics such as quinolones and macrolides; antipsychotics drug such as quetiapine, olanzapine, amitriptyline).

### 5.3 Guidelines combination dose level adjustments in the phase Ib phase

The phase Ib (run-in) phase will be the first 6 patients. This is to monitor the safety of the combination of lenvatinib and eribulin in STS patients. However, this study is not the first study to use the combination of lenvatinib and eribulin in cancer patients. Thus the risk of unexpected DLT may be lower than traditional phase Ib studies. When a safe combination dose is determined, this dose would become the initial dose for the following patients. Dose adjustment for study drugs for adverse events that occur after cycle 1 should follow the protocol guidelines (section 5.4).

#### 5.3.1 Schema for dose adjustments if more than 2 patients have DLT

The first 6 patients will be treated with lenvatinib 18 mg/day D1-D21 and eribulin 1.1 mg/m^2 D1 and D8 (Dose level 11). If no more than 2 ( $\leq 2$ ) patients had dose-limiting toxicity (DLT) in the first cycle (3 weeks), then the lenvatinib (18) and eribulin (1.1) combination will be declared safe. If more than 2 ( $> 2$ ) patients have DLT, the investigators will determine which drug is more pertinent to the DLT(s) and then will follow the customized block chart to shift the dose. If lenvatinib is determined to be related to DLT, the next lower dose would be dose level 21. Otherwise, if eribulin is determined to be the likely cause for DLT, the next dose level will be level 12. The lowest dose acceptable would be either dose level 22 or dose level 31. If still more than 2 patients have DLT in the first 6 patients of dose level 22 or level 31, the combination of lenvatinib and eribulin will be considered too toxic in STS patients.

Table 1: dose levels of lenvatinib and eribulin combination

Dose levels*	Lenvatinib	Eribulin
Dose level 11	18mg/day D1-D21	1.1 mg/m  D1, D8
Dose level 21	14mg/day D1-D21	1.1 mg/m  D1, D8
Dose level 31	10mg/day D1-D21	1.1 mg/m  D1, D8
Dose level 12	18mg/day D1-D21	0.7 mg/m  D1, D8
Dose level 22	14 mg/da D1-D21	0.7 mg/m  D1, D8

[figure not shown]

Figure 2. Schematic dose adjustment directions if more than 2 patients have DLT

The Principal Investigator will be responsible to determine the association as to which drug is more likely to be associated with the DLT and the next dose level to be started in the next step of the phase Ib (run-in) phase.

### 5.3.2 Definitions of DLT

Dose limiting toxicities (DLT) include the following:

- (1) Grade 4 diarrhea
- (2) Grade 3 or higher proteinuria
- (3) Grade 3 or higher hand foot syndrome
- (4) Grade 3 or 4 peripheral neuropathy
- (5) Neutropenia Grade 4 that lasted >5 days
- (6) Neutropenia Grade 3 or 4 complicated by fever and/or infection (Absolute Neutrophil Count [ANC] < 1.0 x 10^9/L, fever ≥38.5°C)
- (7) Thrombocytopenia Grade 4 of any duration
- (8) Thrombocytopenia Grade 3 complicated by bleeding and/or which required platelet or blood transfusion
- (9) Other Grade 3 or 4 clinically significant non-hematologic toxicities (except for inadequately treated nausea and/or vomiting) considered related to study drug
- (10) Failure to administer ≥ 75% of the planned dosage of combination therapy as a result of treatment related (at least possibly related) toxicity during Cycle 1.
- (11) Grade 3 or above hypertension not able to be controlled by medication

- (12) Grade 3 or above gastrointestinal perforation
- (13) Grade 4 hemorrhage
- (14) Grade 3 thromboembolic event
- (15) Grade 3 or above wound dehiscence requiring medical or surgical intervention

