## **4 Study Design**

### **4.1 Overall plan of the study**

This is a single country multi-center, open-label phase Ib/II single-arm study in advanced adipocytic and leiomyosarcoma patients. Patients will be treated with the combination of lenvatinib and eribulin until disease progression, intolerable toxicity, or patient withdrawal.

The first 6 patients will be enrolled in a phase Ib run-in period to evaluate the safety of the combination of lenvatinib and eribulin. If more than 2 patients experience dose-limiting toxicity(s), dose adjustments will be carried out according to a pre-determined plan. If there are still more than 2 patients in the lowest pre-specified dose of combination, the combination would be declared too toxic for further treatment in STS patients.

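### Some DLT items count higher grades and others do not, so a treatment-related death late in cycle 1 can, read literally, go uncounted in the 2-versus-3-of-6 run-in rule (minor)

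*Combined protocol and SAP*

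**What the plan says.** Section 5.3.1 sets the run-in: "The first 6 patients will be treated with lenvatinib 18 mg/day D1-D21", with eribulin on days 1 and 8. The dose passes if no more than two "patients had dose-limiting toxicity (DLT) in the first cycle (3 weeks"). Section 4.1 gives the other branch: "If more than 2 patients experience dose-limiting toxicity(s), dose adjustments will be carried out according to a pre-determined plan".

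Section 5.3.2 lists 15 DLT items, and the synopsis (Study Medication) carries the same 15. They treat the upper grade in two ways.

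- **Open upward:** items 2 (proteinuria), 3 (hand-foot syndrome), 11 (uncontrolled hypertension), 12 and 15 (wound dehiscence). Item 12, for example, reads "12) Grade 3 or above gastrointestinal perforation".
- **Closed:** item 1 (diarrhoea, grade 4), item 13, "13) Grade 4 hemorrhage", item 14, "14) Grade 3 thromboembolic event", and the catch-all item 9, "Other Grade 3 or 4 clinically significant non-hematologic toxicities", which also requires a relation to study drug. Item 4 (neuropathy, grade 3 or 4) is closed too.

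Item 10 scores a patient who received less than 75% of the planned cycle 1 dosage because of related toxicity. No item names death or grade 5.

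The two lead-ins differ. Section 5.3.2 introduces the items as what DLTs include; the synopsis presents them as the definition.

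**The concern.** Five items say explicitly that higher grades count, so the natural reading of the closed items is that higher grades do not. Items 9, 13 and 14 matter most. Haemorrhage and thromboembolism have their own items with a ceiling, and the catch-all that might pick up what they miss has a ceiling as well. On that reading a grade 3 thromboembolic event is a DLT while a fatal one is not.

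What is at stake is the run-in count. The decision depends on two versus three patients out of six, and under section 5.3 the dose found safe becomes the starting dose for later patients. One patient left out of the count is enough to reverse the stated outcome.

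**Working it through.** The documents give no operating characteristics for the run-in rule, so there is no stated figure to reproduce.

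**Inputs.** Six patients, 21 daily lenvatinib doses and two eribulin doses in cycle 1; pass at 0 to 2 DLT patients, change dose level at 3 or more (sections 4.1 and 5.3.1). Item wording is from section 5.3.2 and the synopsis. CTCAE 4.03 is the grading scale (sections 5.4 and 6.3.3). That death is grade 5, separate from grade 4, is the CTCAE convention and is assumed here.

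**Step 1: which fatal events are still scored.**
- Items 11, 12 and 15 have no upper limit.
- Item 6 grades the neutropenia and sets no ceiling on the infection, so a fatal infection with grade 3 or 4 neutropenia counts.
- Item 7 counts any grade 4 thrombocytopenia, including one with a fatal bleed.
- A death first recorded as a separate event at a named grade could be scored at that grade.

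What remains is a related fatal haemorrhage, thromboembolism or other non-haematologic toxicity (including diarrhoea, item 1) that was not recorded earlier at a named grade. Item 4 adds little to a question about fatal events.

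**Step 2: when item 10 stops catching a death.** The documents do not say how the 75% is counted across the two drugs. Assume both eribulin doses have been given on schedule.
- Each drug separately: 0.75 × 21 = 15.75 lenvatinib doses. 15/21 = 71.4% triggers item 10; 16/21 = 76.2% does not. The gap opens after the day 16 dose.
- The two drugs averaged: (1 + d/21)/2 for d lenvatinib doses. d = 10 gives 73.8% and triggers item 10; d = 11 gives 76.2% and does not. The gap opens after the day 11 dose.

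Missed lenvatinib doses move these days later. With death on day 17 and one earlier missed dose, 15/21 = 71.4% and item 10 applies on the first reading.

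**Step 3: grade 4 thromboembolism.** It is outside item 14. It counts only if the word Other in item 9 is taken to cover an ungraded part of an event that has its own item. The text does not settle this.

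**Step 4: effect on the count.** Two scored DLTs plus one unscored death give 2 of 6, which passes. Scoring the death gives 3 of 6, which does not. The reversal needs exactly two scored patients among the other five.

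**Step 5: illustration.** Let p be the true rate of events that should count and u the part left uncounted. Then P(pass) = Σ over k = 0, 1, 2 of C(6,k)(p−u)^k(1−p+u)^(6−k). With all events counted at p = 0.40: 0.6⁶ + 6(0.4)(0.6⁵) + 15(0.4²)(0.6⁴) = 0.0467 + 0.1866 + 0.3110 = 0.544.

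| Uncounted u (points) | Rate scored | P(declared safe) |
|---|---|---|
| 0 | 0.400 | 0.544 |
| 0.5 | 0.395 | 0.555 |
| 1 | 0.390 | 0.565 |
| 2 | 0.380 | 0.586 |
| 5 | 0.350 | 0.647 |

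Both p and u are assumptions.

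**The case against.** The strongest reply has three parts.

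**The list may not be closed.** Section 5.3.2 only says what DLTs include, so an investigator could add a fatal event. This helps in that section, but the synopsis words the same items as the definition. The two lead-ins conflict, and neither says that death counts.

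**There are human checks.** Fatal events are serious adverse events reportable within 24 hours (sections 9.1.2 and 9.3.2), and the two site investigators meet after six patients to decide whether phase II may start (section 10.6). A reader might infer from the list that the trial would proceed automatically after a death. The documents do not support that, because the meeting could stop it. But the meeting has no stated criterion and does not alter the DLT count.

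**The scenario is narrow.** The death must be treatment-related, fall late in cycle 1 after nearly full dosing, escape items 6, 7, 11, 12 and 15, and not have been recorded at a named grade beforehand. This stands, and it is why the point is minor.

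Two further readings go too far. One is that grade 4 thromboembolism is definitely excluded; item 9 may cover it. The other is that the chance of wrongly passing the dose rises from 0.544 to 0.647. That needs 5 percentage points of late, otherwise unscored deaths, which is one patient in 20, and nothing in the documents supports that rate. At 0.5 to 1 point the figure is 0.555 to 0.565.

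**Conclusion.** The inconsistency stands as a minor drafting fault with a possible effect on a decision rule. Followed literally, items 9, 13 and 14, and item 1 for diarrhoea, leave a related late cycle 1 death uncounted, and one such patient can change the stated outcome from dose adjustment to safe. That single-patient reversal does not depend on any assumed rate. How often it would happen cannot be derived from the documents; a small shift in the chance of passing, about one to two percentage points at an assumed 40% true rate, is more plausible than a large one.

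The conclusion rests on three things: death being grade 5 by CTCAE convention, the synopsis wording being taken as closed, and one of the two readings of item 10, which decides whether the gap opens after about day 16 or about day 11. It does not extend to fatal toxicity in general, since several items and an early shortfall in dosing still catch such events.

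**What to change.** In section 5.3.2 and the synopsis, reconcile the upper grade limits of items 1, 9, 13 and 14 with those of the open-ended items. State for each whether higher grades, including fatal events, count, and whether item 9 covers grades of a listed event that its own item leaves out. Align the two lead-ins so that both present the list as either closed or open. If the run-in is already complete, report how any such event was counted.

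The choice of clinical thresholds remains with the sponsor. The cost is a few words in two places, with no change to the sample size or to the run-in rule itself.

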### 5.3.3 Decision on Final Phase II dose

The final phase II dose will depend on the final result from the phase Ib part, as to which dose level did the phase Ib part confirmed to be safe (Dose 11 or 12 or 21, etc). Patients who received the same dose as to the phase II part will be included into part of the phase II efficacy analysis. (Please also refer to section 10.6 on how two institutions collaborate and determine on this issue)

## 5.4 Guidelines for dose delays and dose modifications

This part for the guideline is for all phase Ib and phase II patients..

Dose modification is made according to the greatest degree of toxicity that is graded base on Common Terminology Criteria for Adverse Events v4.03 (CTCAE). The CTCAE v4.03 can be downloaded from the CTEP home page. All appropriate treatment areas should have access to a copy of the CTCAE v4.03.

([http://ctep.cancer.gov/protocolDevelopment/electronic\\_applications/ctc.htm#ctc\\_40](http://ctep.cancer.gov/protocolDevelopment/electronic_applications/ctc.htm#ctc_40)).

### 5.4.1 Hematological toxicities

Toxicity	Adverse event	Dose Reduction/Delay	
		Eribulin	Lenvatinib
Hematologic toxicity attributed to any or all treatment	ANC <1000/mm  or Platelets 25000-74999/mm  within 3 days prior to scheduled therapy	If Day 1: Hold until recovery to ANC >1000/mm  and Platelets >75000/mm  . Resume at same level after recovery If Day 8: Hold until recovery to ANC >1000/mm  and Platelets > 75000/mm  . Resume at same level after recovery	Hold until recovery to ANC > 500/mm  and platelets more than 25000/ mm  , Resume at same level after recovery.
	Platelets <25000/ mm  or Platelets 25000-50000/ mm  complicated	If Day 1: Hold until recovery to Platelets > 75000/ mm  . Resume at same level after recovery	Hold until recovery of Platelets 25000/mm  . Resume at current

	by bleeding, easy bruising, petechiae, or requiring platelet transfusion	If Day 8: Hold until recovery to Platelets > 75000/ mm  . Resume at same level after recovery	dose level.
	Prolonged neutropenia (ANC<500/ mm  for >7 days)	Hold until recovery to ANC>1000/ mm  . Resume at one dose level below current dose level	Hold until recovery to ANC>500/ mm  Resume at same level dose.
	Febrile neutropenia (ANC <1000/ mm  with temperature of >38.5°C)	Hold until recovery to ANC>1000/ mm  . Resume at one dose level below current dose level	Hold until recovery to ANC>1000/ mm  . Resume at same dose level
	Anemia	No reduction or delay	No reduction of delay

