#### 5.4.2 Non-hematological toxicities

Toxicity	Adverse event	Dose Reduction/Delay	
		Eribulin	Lenvatinib
Hepatic toxicities	Grade 3/4 toxicity of AST/ALT/ Total bilirubin	If during treatment there is grade 3/4 liver toxicity then dose reduce by 1 dose level.	Hold until recovery to Grade 1 or baseline. Resume at reduced dose of 14 mg po daily if first occurrence, reduce to 10 mg po daily on second occurrence and 8 mg po daily on third occurrence.
Peripheral neuropathy	Grade 3 or 4	Hold until recover to ≤ grade 2. Reduce dose by one dose level. If neuropathy fails to recover to grade 2 within 3 weeks, eribulin should be discontinued.	No modifications necessary
Nonhematologic toxicity grade 3 or 4 attributed	Grade 3 or 4 nausea/ vomiting despite optimal	Hold until nausea/ vomiting have resolved to	Hold until nausea/ vomiting have resolved to ≤ grade 1. Resume at same

to any or all treatment (except for neuropathy)	antiemetic treatment	≤ grade 1. Resume at same dose level.	dose
	> Grade 2 stomatitis	Hold until stomatitis has resolved to ≤ Grade 1. Resume at one dose level below current dose level	Hold until recovery to ≤ grade 1. Resume at the same dose level
Hypertension	Grade 3 hypertension or life-threatening hypertension	No dose modification necessary	Withhold lenvatinib for Grade 3 hypertension that persists despite optimal antihypertensive therapy; resume at one dose level below current dose level. Discontinue for life-threatening hypertension
Cardiac dysfunction or hemorrhage	Grade 3 or 4 events	No dose modification necessary	Withhold lenvatinib for the development of Grade 3 event until improved to Grade 0 or 1 or baseline. Either resume at a reduced dose or discontinue lenvatinib depending on the severity and persistence of the adverse event
Proteinuria	Grade 3 or nephrotic syndrome (see footnote)	No dose modification necessary	Withhold lenvatinib until ≤ Grade 2 (proteinuria 2+ or 3+ or 24-hour urinary protein < 3.5g). Resume at next dose below current dose. Discontinue lenvatinib if nephrotic syndrome.
QTc prolongation	Grade 3 or greater	No dose modification necessary	Monitor and correct electrolyte abnormalities in all patients. Withhold lenvatinib for the development of Grade 3 or

			greater QT interval prolongation. Resume lenvatinib at one dose level below the current dose when QTc prolongation resolves to Grade 0 or 1.

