Hand foot syndrome	Grade 2	No modification necessary	Withhold until $\leq$ Grade 1. Resume at the same dose or below current dose at physicians discretion
	Grade 3/4	No modification necessary	Withhold until $\leq$ Grade 1. May resume at the same dose or below current dose at physicians discretion

- For other grade 3/4 non-hematological toxicities not specifically mentioned in the table: the investigator could decrease the dose of the responsible drug after returning to grade 1 at the physician's discretion.
- If a patient has simultaneous multiple grade 2 adverse events or an intolerable grade 2 adverse events as per CTCAE, the investigator could decrease the dose of the responsible drug after discussion with the Principal Investigator and adjust according to 5.4.3.
- Proteinuria: Grade 2: urine dipstick proteinuria 2+ and 3+; if urine dipstick proteinuria 4+, check 24-hour urine protein, if  $\geq$  3.5g/day, confirms grade 3 proteinuria. If  $<$ 3.5 g/day, follow grade 2 proteinuria schedule

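### In the second platelet row of section 5.4.1, the lenvatinib hold for 25,000-50,000/mm³ with a bleeding sign or transfusion ends at a count already met when it starts, and signs below Grade 3 need not clear

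*Combined protocol and SAP*

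**What the plan says.** Section 5.4 opens with "This part for the guideline is for all phase Ib and phase II patients", so its tables govern every patient. In section 5.4.1 the second row has two limbs:

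- platelets below 25,000/mm³, on the count alone;
- platelets 25,000-50,000/mm³, complicated "by bleeding, easy bruising, petechiae, or requiring platelet transfusion".

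The lenvatinib cell gives a single release for both limbs, "Hold until recovery of Platelets 25000/mm"³, followed by the current dose level. The eribulin cell of the same row releases above 75,000/mm³. The row above it covers platelets 25,000-74,999/mm³, but only for counts "within 3 days prior to scheduled therapy", and releases lenvatinib above 25,000/mm³.

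Section 5.4.2 has a separate row for Grade 3 or 4 cardiac dysfunction or hemorrhage: "Withhold lenvatinib for the development of Grade 3 event until improved to Grade 0 or 1 or baseline".

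Two DLT items in section 5.3.2 are relevant. Item 8 is "Thrombocytopenia Grade 3 complicated by bleeding and/or which required platelet or blood transfusion". Item 10 is failure to give at least 75% "of the planned dosage of combination therapy as a result of treatment related (at least possibly related) toxicity during Cycle 1".

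**The concern.** The complicated limb picks out patients by clinical signs as well as by count, but its lenvatinib release ignores the signs and uses the lowest count in the trigger range. The hold therefore has no usable end point. Read literally, a thrombocytopenic patient who is still bruising or oozing can restart lenvatinib at the current dose level.

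The written rule matters because lenvatinib is taken daily at home (section 5.1), while laboratory tests are scheduled only before days 1 and 8 (section 5.2).

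There is a smaller statistical consequence. How long a hold lasts feeds the frequency of dose interruptions listed in section 2 and, in cycle 1, DLT item 10. If the plan does not define when a hold ends, clinicians could hold similar patients for different times.

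**Working it through.** **1. Trigger against lenvatinib release, section 5.4.1 (counts per mm³).**

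| Row | Trigger | Lenvatinib release | Already met at the trigger? |
|---|---|---|---|
| 1 | ANC below 1,000, or platelets 25,000-74,999, before scheduled therapy | ANC above 500 and platelets above 25,000 | On platelets, yes, except at exactly 25,000 |
| 2, count limb | Platelets below 25,000 | 25,000 | No |
| 2, complicated limb | Platelets 25,000-50,000 with a sign or transfusion | 25,000 | Yes, across the whole range |
| 3 | ANC below 500 for more than 7 days | ANC above 500 | No |
| 4 | ANC below 1,000 with fever | ANC above 1,000 | No |

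Reading the row 2 release as strictly above 25,000 changes the answer only for a count of exactly 25,000. The row 2 eribulin release, above 75,000, lies beyond the whole trigger range and works.

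**2. Does another rule require the complication to clear?**

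- Grade 3 hemorrhage: yes, section 5.4.2. That row's trigger also names Grade 4, although its withholding sentence speaks only of Grade 3. I do not count Grade 4 bleeding in the gap.
- Bleeding below Grade 3, bruising, petechiae, or transfusion need alone: no mandatory rule. The note beginning "If a patient has simultaneous multiple grade 2 adverse events or an intolerable grade 2 adverse events as per CTCAE" permits a dose reduction but does not require one. Section 5.5 leaves stopping for safety to the treating physician.
- CTCAE v4.03 is not reproduced, so the documents do not show which transfused bleeds fall below Grade 3.

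**3. Worked patient.** Platelets are 40,000 with petechiae on day 12 of cycle 1, outside row 1's window. Only row 2 applies. The release count of 25,000 is already exceeded, and the petechiae play no part in the release.

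**4. Hold length and DLT item 10.** The item does not say whether the 75% applies to each drug or to the two combined.

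*Per drug.* Planned lenvatinib is 18 mg × 21 = 378 mg, and 75% is 283.5 mg.

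- 5 days missed: 16 × 18 = 288 mg, 76.2%, not a DLT.
- 6 days missed: 15 × 18 = 270 mg, 71.4%, a DLT.

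The limit is the same at 14 or 10 mg/day, because the fractions 16/21 and 15/21 do not depend on dose.

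*Mean of the two relative doses, full eribulin given.*

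- 10 days missed: (11/21 + 1)/2 = 76.2%, not a DLT.
- 11 days missed: (10/21 + 1)/2 = 73.8%, a DLT.

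The day-12 patient can miss at most 10 doses (days 12-21). That is 11/21 = 52.4% per drug, a DLT, but 76.2% on the mean, not a DLT.

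*Low count before day 8.* Row 2 then holds eribulin too, so full eribulin cannot be assumed. If day 8 is omitted, eribulin is at 50% and fails per drug whatever happens to lenvatinib. On the mean reading, full lenvatinib gives (1 + 0.5)/2 = 75.0%, just acceptable, and one missed dose gives (20/21 + 0.5)/2 = 72.6%.

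**The case against.** **The cell may not mean immediate release.** A patient at 25,000-50,000 who is still bleeding still meets the trigger, so the hold can be read as continuing. Alternatively, 25,000 may be a deliberate floor for lenvatinib, as row 1 suggests. This stands to the extent that the wording is ambiguous, and a mandated unsafe restart is not shown. It does not rescue the cell. If 25,000 is a floor, the complicated limb does nothing for lenvatinib. If the hold lasts until the trigger clears, 25,000 is the wrong end point. The text needs changing on either intent.

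**Serious bleeding is covered.** This stands in full. A reader might infer that the plan lets lenvatinib restart during any bleeding. Section 5.4.2 rules that out for Grade 3 hemorrhage, and section 5.4 makes the greatest degree of toxicity govern.

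**The DLT consequence is thin.** This largely stands. A reader might infer that the cell threatens the phase Ib decision. Item 8 names Grade 3 thrombocytopenia with bleeding or transfusion. If the row's range corresponds to that grade (an assumption, since CTCAE is not reproduced), hold length matters mainly for bruising or petechiae alone. The arithmetic also depends on an unstated reading of item 10. Section 10.6 has both site investigators meet after six patients before phase II starts, so divergence between sites is possible but not shown.

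**Clinicians will use judgment.** They may, and section 6.3.3 allows toxicity evaluation at any time. That limits the harm but does not supply the missing end point.

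**Conclusion.** The point holds in limited form. For platelets 25,000-50,000/mm³ with a listed complication, the lenvatinib release is met when the hold starts and resolution is not required. The gap covers bleeding below Grade 3, bruising, petechiae, or transfusion need alone. It is a dosing-safety defect worth correcting. It does not affect the primary analysis: the response-rate endpoint, the Simon stopping rule and the sample size are unchanged.

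Its frequency cannot be sized, because the documents give no rate for such events. The effect on DLT counting is secondary and confined to cycle 1.

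A reader might also infer that the release must be set above 50,000. The documents do not support that. A patient at 40,000 whose petechiae had cleared would stay held, although row 2 does not hold an uncomplicated patient at that count and row 1 releases lenvatinib above 25,000.

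**What to change.** Split the lenvatinib cell in row 2. Leave the limb below 25,000/mm³ as it is. For the complicated limb, hold lenvatinib until bleeding signs have resolved and there is no ongoing need for platelet transfusion, with platelets above 25,000/mm³, then resume at the current dose level. The sponsor's clinicians may choose a higher release count, for example above 50,000/mm³, provided they align row 1 with it. If 25,000 is meant as a lenvatinib floor in row 1, say so there.

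Require an unscheduled repeat count during the hold. Without one, a hold from day 8 to the next scheduled day 1 test would miss 14 of 21 doses, leaving 7/21 = 33.3%.

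The amendment is small. Its cost is a somewhat longer lenvatinib interruption in the affected patients. In cycle 1, 6 or more missed days would meet item 10 on the per-drug reading, and more than 2 patients with DLTs among 6 leads to a lower dose level (section 5.3.1). In later cycles a long hold could count toward the limit of two consecutive held cycles in section 5.5.
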